1.1. Primary Objective

The **primary objective** of the trial is to evaluate the two-year relapse-free survival (RFS) of patients with poor-risk Acute Myeloid Leukemia (AML) or Myelodysplasia (MDS), who receive maintenance treatment with 5-Azacytidine(5AC) in combination with GM-CSF during remission, following definitive therapy with either a stem cell transplant (SCT) or consolidation chemotherapy.

1.2. Secondary Objectives

1. Describe and quantify the toxicity profile of the combination of 5AC and GM-CSF
2. Determine the impact on one-year RFS and overall survival for poor-risk myeloid disorders following maintenance therapy with 5AC and GM-CSF
3. Describe the changes in the clonogenic population during maintenance therapy, including changes in detectable cytogenetic abnormalities in blood and marrow.

2. Background

2.1. Introduction

Myeloid disorders remain a challenge for clinicians to effectively treat. Patients with AML, despite good initial responses to standard induction therapy, usually experience long term treatment failure with standard chemotherapy, particularly in patients with poor-risk disease, which includes AML arising out of MDS, treatment-related disease, AML associated with unfavorable karyotypes or FLT3/ITD mutations, and relapsed or refractory disease. Reported five-year survival rates are 15-30% with chemotherapy alone,¹ with survival rates less than 10% in poor-risk AML and only 24% in intermediate-risk disease.² In treatment-related AML, median survival is reported at only 10 months, with a 10% five-year overall survival.³ Relapse is the primary reason for these dismal outcomes: 92% of patients classified as high-risk experience relapse, as do 61% of the intermediate-risk group. Allogenic hematopoietic stem cell transplant (allo SCT) is often the only curative option for poor-risk AML and MDS. Unfortunately, even allo SCT has limited efficacy, with studies demonstrating only 40% survival at four years,⁴ with approximately 40% relapse rates.⁵⁻⁸

Patients who relapse after allo SCT have a dismal prognosis with a median survival of only three to four months without further therapy, and only twelve months with therapy.⁹ This is in part due to the rapid rate of relapse. Studies demonstrate that up to half of all relapses occur within one year after transplant, with fully 80% occurring within 24 months.⁶⁻¹⁰ Further contributing to poor survival are the limited treatment options at relapse, which include donor lymphocyte infusion (DLI), a second stem cell transplant, additional traditional chemotherapy, or newer biologically targeted agents (e.g., histone deacetylase inhibitors, DNA methyltransferase inhibitors, FLT3 inhibitors, and others). The only proven curative options are DLI or a second allo SCT, though few patients are candidates for these

[figure not shown]
treatments and those that do undergo salvage SCTs have poor outcomes, with median overall survival under 12 months.^{11;12} The success of salvage chemotherapy following allo SCT is also limited, as approximately one third of patients achieve a CR, and median disease-free survival (DFS) is just six months.¹² Due to the high relapse rate, the dismal prognosis at relapse, and the speed with which relapse occurs, novel therapies are clearly needed to maintain remission after treatment with allo SCT and traditional chemotherapy. Effective maintenance therapies would need to target and possibly eliminate the undetectable residual disease that is suspected responsible for relapse.

Pediatric patients with AML who relapse after blood or marrow transplantation (BMT) have poor outcomes.^{68;69} Therapies preventing relapse would be beneficial in children as well as adults. Pediatric patients with other high-risk malignancies who are in remission after BMT have been treated safely and successfully with regimens that include GM-CSF.^{70;71} In these studies, doses of GM-CSF were higher than the proposed maximum allowable dose proscribed below, 125micrograms/m², and were tolerated with limited toxicity.

2.2. Cancer Stem Cells

One proposed theory that may explain the high treatment failure and relapse rate following successful initial treatment of leukemia surrounds cancer stem cells. Our group has identified a population of cells that appears responsible for relapse in AML. This population of cells, not identified in normal bone marrows, is present at both diagnosis and relapse in patients with AML. When it is detected in patients in CR, it predicts relapse of their AML (Figure 2). Cells in this population share properties with both normal and leukemia stem cells (LSCs): they are phenotypically and functionally primitive, capable of both self renewal and multi-lineage differentiation; they are quiescent and relatively drug resistant, therefore difficult to eradicate by traditional cytotoxic chemotherapy and SCT regimens.¹³⁻¹⁵ These cytotoxic therapies effectively target and eliminate the bulk leukemic blasts cells that are biologically distinct from LSCs. The population of residual LSCs appears to persist even throughout CR and, left untreated, results in relapse. It is this population of putative LSC's that is the proposed target in this study.

Figure 1

2.3. Maintenance Therapy in Leukemia

To prevent relapse, therapy must target and eradicate residual leukemia. One proposed mechanism to eradicate the LSC population is to preferentially drive those cells toward differentiation to a more mature progeny and eliminate the self-renewal capacity of the clone. Such differentiated cells are susceptible to apoptosis. Therefore, maintaining pressure towards differentiation would presumably eventually exhaust the clone and its ability to cause relapse. Our group has studied differentiation therapy and the role of combination strategies that are driven by growth factors rather than cytotoxic chemotherapy. This approach may be particularly well suited to maintenance therapy as it activates an important stem cell pathway that renders the progenitor with limited ability to self-renew.^{16;17} Such long term, differentiation pressure would be expected to eradicate the malignant stem cell clone. There is evidence that this approach is effective in other leukemias.

Unfortunately, the only leukemias in which maintenance therapy has proven effective are Acute Promyelocytic Leukemia (APL) and low-risk acute lymphocytic leukemia (ALL).^{18;19}

Typically, maintenance therapy in leukemia employs agents similar to those in induction therapy, but at lower doses over one to two years. Maintenance therapy for both APL and ALL typically consists of a regimen containing low-dose 6-mercaptopurine (6-MP) and (MTX) for one to two years.²⁰ Interestingly, the mechanism of action of these agents at these low maintenance doses is unclear. However, our group has shown that 6-MP and MTX differentiate ALL and APL cells *in vitro*.¹⁶ Furthermore, APL maintenance therapy consists of ATRA, a known differentiating agent. This suggests that the mechanism of action of this maintenance therapy may at least in part be through induction of terminal differentiation and subsequent exhaustion of the LSC clone responsible for disease initiation and relapse.

2.4. Differentiation Therapy

We hypothesize that inducing myeloid differentiation of the LSC's over a prolonged course could exhaust the leukemic clone in AML and MDS. There are several types of differentiating agents that are active in myeloid diseases that employ different mechanisms of action, including: MS-275, a histone deacetylase inhibitor (HDACi); Bexarotene, a retinoid X receptor; Azacytidine, a DNA methyltransferase inhibitor; Bryostatins, a protein kinase C modulator. In general these act by restoring the capacity for cellular differentiation that the malignant clone has lost.²¹ Though these differentiating agents show substantial activity *in vitro*, they are only modestly active clinically. Our group has previously shown that the ability to inhibit cell cycling appears to be a critical property of most pharmacologic differentiating agents regardless of their presumed mechanism of action; moreover, these agents require growth factors to induce terminal differentiation.²² Most *in vitro* studies are performed with serum, which contains growth factors, which could account for the disparity in results. Our preclinical studies support this, as the addition of growth factors (GM-CSF) results in enhanced differentiation compared to these differentiating agents alone, demonstrated both by a decrease in clonogenic capacity and a change in cellular phenotype.^{16,23}

2.5. Methylation Affects Differentiation in Myeloid Malignancies

The DNA methyltransferase inhibitors act via hypomethylation and epigenetic modulation. Studies have demonstrated that methylation of CpG dinucleotides in the promoter regions of cell regulatory genes is associated with gene silencing, and these changes are present in a variety of cancers, leading to loss of differentiation capacity and other critical functions.²¹ Promoter methylation of this type is relatively cancer-specific, making DNA methylation an attractive target for oncology therapeutics. In malignant myeloid cells the most widely reported methylated gene is the cyclin dependent kinase inhibitor p15^{INK4B}, with methylation of this gene reported in up to 68% of primary AML samples.²⁴⁻³⁰ Other genes that are methylated in myeloid malignancies include E-cadherin, p73 and RAR α , which are all implicated in hematopoietic differentiation.^{31,32} Azacytidine causes hypomethylation and therefore reactivation of previously silenced genes involved in cellular differentiation, particularly P21, causing differentiation of leukemic cells.²¹ Furthermore, data suggest that there is increased hypomethylation at lower doses of 5AC. (Hollenbach et al. e9001) In fact

azacytidine, a pyrimidine analog and antimetabolite, has cytotoxic effects at higher doses as opposed to differentiating effects at lower doses.

2.6. Clinical Studies of 5AC in AML/MDS

The first clinical trials of 5AC in AML met with only marginal success.³³ However, these trials used high cytotoxic doses of 5AC (150-750mg/m² per dose; 750–2500mg/m² per cycle). More recently studies have focused on the utilization of lower doses of 5AC in an attempt to promote differentiation activity.³³ Initial clinical studies of the drug at low doses were done in MDS. Phase III studies of 5AC and DAC in patients with MDS using lower doses (45-75mg/m² per dose; 135mg/m² -525mg/m² per cycle) demonstrated response rates of 52-60%.³⁴⁻³⁶ Data from these studies resulted in the FDA approval of 5AC and DAC for the treatment of CMMoL and MDS. In 2002, a CALGB phase III trial of 5AC versus supportive care, in 194 patients with high-risk MDS, reported significantly higher response rates and improved survival in the treated group. In a larger, randomized, open-label trial in patients with high-risk MDS, Fenaux demonstrated an improved overall survival in those treated with 5AC compared to the those treated with supportive care, 24.5 months versus 15 months.³⁷ Building upon the success in MDS, investigators now use low-dose 5AC in AML studies.

Recently several groups have reported that low dose 5AC has clinical activity in AML. These data are summarized in Table 1.^{35;37-40;40-43} In a retrospective series, Sudan observed a statistically significant increase in overall survival with 5AC in patients with AML.⁴⁰ Al-Ali demonstrated activity in patients with relapsed AML with 65% response rates.⁴⁴ DAC proved active in patients with MDS and AML, all but one with refractory or relapsed disease.^{39;45} Several groups advanced these agents to first line treatment in patients older than 60, who often cannot tolerate standard cytotoxic therapy. The results are promising, with response rates as high as 65 % and complete remission rates reaching 63 % in patients receiving doses of 20mg/m² for longer periods of time.⁴¹⁻⁴³

Table 1

Study	Rx	Population	Dose	No pts	Response	Comments
Sudan et al. Cancer 2006	5AC	AML, retrospective evaluation	75mg/m ² sq daily x 7 days q 28d	20	60% (12/20), 4CR, 5PR, 3HI	Survival >15mo responders vs 2.5mo non-responders (p <0.009)
Al-Ali, HK et al. Blood 2006.	5AC	AML de novo, relapsed	75mg/m ² sq daily x 5 days q 28d	17	65% (11/17), 6CR, 2PR, 2HI. Cytogenetic remission in 2 patients	Duration of response 18 wks (15-not yet reached)
Issa et al. Blood 2004	DAC	AML/MDS, relapsed, refractory	5-20mg/m ² IV X 10 -20 days	44	27%(12/44) 7CR,5HI	9 of 12 responders treated at 15mg/m ² x 10days
Lubbert et al. ASH abstract 2007	DAC	AML, untreated	45mg/m ² IV x 3 days x 4; 20mg/m ² x3 days	155	54%(83/155) 23CR, 15PR, 45 ALE	Cr in 15%, ATRA in cycle for ALE or stable dz (69); 41 rec'd maintenance 20mg/m ² x3days, every 6-8 weeks
Blum et al. PNAS 2010	DAC	AML, untreated	20mg/m ² IVx10 days	53	64%(34/53) 25CR,iCR	CR in 47%, median 3 cycles
Cashen et al. JCO 2010	DAC	AML, untreated	20mg/m ² x 5days	55	25%(14/55) 13CR,1iCR	Median 3 cycles, up to 25 cycles

Abbreviations: CR=complete response, iCR=incomplete response, HI=hematologic improvement, PR=partial response, ALE=anti-leukemic effect

Because 5AC demonstrated activity in disease that relapsed after standard therapy, its role in post-SCT relapse was investigated. Recently there have been multiple reports of low-dose 5AC used as salvage treatment for relapse after SCT. One of the initial reports involved a patient who had relapsed after SCT, then achieved a CR after treatment with five cycles of 5AC, subsequently received DLI, and remained in CR four months later.⁴⁶ In a series of 26 patients who received one cycle of 5AC followed immediately by DLI, two-thirds of the patients responded, a marked improvement over the historical response rate of 10-40%.⁴⁷ In different group of nine patients, five patients responded to 5AC, four of whom had overall survival greater than 12 months.¹⁰ Although four of the nine patients did not respond to 5AC, they had all had refractory disease at time of SCT. Recently our group reported a series of 37 patients who had relapsed after transplant, 10 of whom received 5AC as salvage therapy. Six of the ten patients achieved CR, only two of whom had received DLI. Five of those patients remain disease-free compared to only five of the 27 patients who did not receive 5AC.

[figure not shown]
2.7. 5AC as Maintenance Therapy

Due to these favorable responses to salvage treatment after both standard treatment and SCT, together with a favorable toxicity profile, investigators began to pursue the use of low-dose azacytidine as maintenance treatment in patients with AML who were at high risk of relapse. Lubbert incorporated maintenance treatment with DAC in patients who achieved responses after initial induction therapy with the agent. With this paradigm, 57 patients received maintenance therapy, 71% of whom were in either CR or PR. They observed little toxicity and prolonged remission rates.⁴⁸ 5AC was also studied as maintenance after successful induction therapy in patients with AML or MDS; 23 patients over the age of 54 received the drug and, when compared to age-matched historical controls, experienced longer duration of CR and OS.⁴⁹ Jabbour used 5AC as maintenance treatment to prevent relapse after SCT.¹⁰ The eight patients who received maintenance therapy had disease that was exceptionally high-risk for relapse: at time of transplant four had refractory disease, one was in CR2, and two were in CR3. Of the eight patients who received maintenance therapy, three are in complete remission after more than two years, and the only death was at 25 months. A larger dose finding study of 45 patients who received 5AC as maintenance therapy after SCT revealed a one-year event-free and overall survival of 58% and 77%, respectively.⁵⁰ These results demonstrate that 5AC could be a promising therapy not only for relapse after SCT, but perhaps have greater efficacy in a maintenance setting. Therefore, 5AC used as maintenance therapy after SCT warrants evaluation in a clinical trial.

2.8. Preclinical Studies of 5AC and GM-CSF

Our preclinical studies demonstrated that after exposure to 5AC, the AML cell line KG1 showed evidence of phenotypic differentiation, with a decrease in expression of CD34 and an increase in expression CD33. The addition of GM-CSF augmented this differentiating effect (Figure 2).

Figure 2

5AC exposure leads to differentiated cells in the AML cell line KG1, demonstrated by increased expression of CD33 and decreased expression of CD34, a phenotype characteristic of more mature myeloid cells than in the control. This differentiation is enhanced by the addition of GM-CSF.

2.9. Clinical Studies with Differentiating Agents and GM-CSF

Our group has built upon such preclinical data and has focused on studying numerous agents with differentiating properties. A phase I trial of the differentiating agent Bryostatins with GM-CSF demonstrated clinical activity in refractory myeloid malignancies but was intolerable at biologically active doses.⁵¹ Subsequently, a Phase I study with MS-275 showed clinical activity and evidence of differentiation.⁴⁵ In a Phase II study of MS-275 and GM-CSF in patients with high-risk MDS or relapsed and refractory AML, 21% of patients achieved a response and demonstrated clinical evidence of differentiation.⁵² We propose a phase II study to determine the impact of maintenance therapy with 5-azacytidine and GM-CSF in patients with poor-risk AML or MDS, who are in remission after definitive treatment with either stem cell transplant or consolidation chemotherapy.

In order to precede relapse and to avoid lead time bias, treatment would need to commence within 185 days of definitive therapy. Furthermore, approximately 50% of relapses occur within the first year and up to 80% within two years after SCT, therefore we would limit the duration of maintenance therapy to one year, followed by two years of follow-up.

3. Patient Selection and Enrollment

3.1. Inclusion Criteria

1. Age \geq 0.5 years
2. Initial diagnosis of poor -risk AML or MDS (defined in section 3.2), treated with either stem cell transplant or consolidation chemotherapy, within the past 60-185 days
3. ECOG performance status 0-2
4. No morphologic evidence of leukemia or active MDS as determined by JHH Hematopathologist independent review of a bone marrow aspirate and biopsy done following the completion of therapy.
5. Peripheral blood count recovery: Neutrophil count \geq 1000 / μ L, platelet count \geq 50x 10⁹ / μ L without platelet transfusions, and adequate hematocrit independent of red cell transfusions .
6. No evidence of extramedullary leukemia, such as CNS or soft tissue involvement
7. Adequate end organ function as measured by the following: AST and ALT \leq 4 x normal, total serum bilirubin $<$ 2 x upper limit normal (unless due to hemolysis, Gilbert's syndrome, or ineffective erythropoiesis), creatinine \leq 2 x upper limit of normal
8. Ability to give informed consent
9. In agreement to use an effective barrier method of birth control to avoid pregnancy during the study and for a minimum of 30 days after study treatment, for all male and female patients who are fertile

3.2. Inclusion Criteria Definitions

The original diagnosis of AML or MDS must have been confirmed by bone marrow aspirate and/or biopsy review by a JHH Hematopathologist. Poor-risk AML is defined as disease that is therapy-related or arises from a previous marrow disorder, or *de novo* AML that is associated with any of the following characteristics: patient age 60 years or greater, trilineage dysplasia, disease status greater than or equal to CR2, FLT3/ITD mutations, detectable disease at time of consolidation chemotherapy or SCT, or poor-risk cytogenetics, which include abnormalities of chromosome 3, 5, or 7, trisomy 8, 11q23 abnormalities, t(6;9), 20q-, and complex karyotype.

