5.4. Duration of Follow-up

Patients will be followed for relapse and death for three years from the first day of the first cycle of treatment. Patients are routinely followed and monitored by JH physicians after SCT or chemotherapy, and patients who complete the study and continue to receive their care at JH will have survival captured annually at least.

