9.1. Objectives

9.1.1. Primary Objective

The **primary objective** of the trial is to evaluate the two year relapse-free survival (RFS) of maintenance treatment with 5AC in combination with GM-CSF in patients with poor-risk Acute Myeloid Leukemia (AML) and Myelodysplasia (MDS) in

complete remission after definitive therapy with either a stem cell transplant or consolidation therapy with chemotherapy. RFS will be defined as time to relapse or death. The start time of RFS will be the date of first remission marrow following induction treatment. Patients will be required to have no morphologic evidence of leukemia or active MDS before entry onto the protocol. This study will monitor three separate cohorts:

1. Patients in complete remission (CR) following a full myeloablative stem cell transplant
2. Patients in CR following a non-myeloablative stem cell transplant
3. Patients in CR following standard consolidation therapy

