9.2. Study Design

This will be a three-arm phase II study with historical references for each arm. The historical two-year RFS and corresponding event rates in these arms are assumed to be: myeloablative, 40% (0.46 per person year); non-myeloablative, 34% (0.54 per person year); and standard consolidation, 20% (0.80 per person year). The non-parametric Kaplan-Meier estimate will be used to monitor the relapse-free survival function in each cohort.

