9.4. Early Stopping Guideline for Futility and Simulations for Each Cohort

The simulation studies demonstrate the power for a sample size of 25 in each cohort. The study will be monitored for futility with a primary endpoint of two-year RFS. If the study meets the accrual goal of 10 patients per year per arm, 20 patients would be accrued by the time the first patient enrolled on study reaches the two-year efficacy endpoint. We will therefore monitor the study based on one-year RFS, knowing that if the one-year RFS is convincingly less than our targeted RFS at two years, the study would not meet its efficacy

objective and the trial should be halted. The non-parametric Kaplan-Meier estimate will be used to estimate the RFS function at one year.

The sample size of 25 and the study design operating characteristics assume a 2.5 year accrual period with an additional follow-up of one year. The null two-year RFS is 40% in the myeloablative group, 34% in the non-myeloablative group and 20% in the non-transplant cohort. We have designed each arm to stop early only if the posterior probability is 70% or higher that one-year RFS is less than that arm's null two-year RFS. Simulations were carried out with exponential survival and staggered patient entry. We assumed on average 10 patients will enter each arm of the study per year. Initial interim analyses occurred after 10 patients enrolled and was repeated every 5th patient to the maximum of 25. The interim analysis estimates of one-year RFS are based on analyses with an underlying Dirichlet process prior. We approximate the posterior distribution, which is actually a mixture of Beta distributions, the mixture depending on the amount of censoring, with a single Beta distribution. The parameters of this posterior Beta distribution are based on the number of failures and the effective sample size at one year, combined with the parameters of the prior.

The following tables summarize the operating characteristics under various scenarios for the underlying exponential RFS, based on 1000 simulations. The uncertainty of the null two-year RFS estimates are characterized with three priors: beta(2,3) in the myeloablative group (Table 5) and beta(2,4) in the non-myeloablative group (Table 6) and beta(1,4) in the non-transplant group (Table 7). This implies that our prior guess at the two year RFS for these three cohorts are respectively 40, 34 and 20%.

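### Patients in CR2 or later are eligible, but section 9.1.1 starts RFS at the first remission marrow after induction and does not say which remission or which relapse applies to them

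*Combined protocol and SAP*

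**What the plan says.** All references are to the combined protocol and SAP.

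- **Eligibility.** Section 3.2 lists among the qualifying features of de novo AML "disease status greater than or equal to CR2, FLT3/ITD mutations, detectable disease at time of consolidation chemotherapy or SCT". The exclusion criteria in section 3.3 do not remove patients in second or later remission. Section 3.1 requires that patients were "treated with either stem cell transplant or consolidation chemotherapy, within the past 60-185 days".
- **Origin.** Section 9.1.1: "The start time of RFS will be the date of first remission marrow following induction treatment". This single rule covers all three cohorts.
- **Event.** Section 9.1.1: "RFS will be defined as time to relapse or death". Section 6.1 defines relapse after complete remission, but does not say which remission.
- **Entry condition.** Section 9.1.1: "Patients will be required to have no morphologic evidence of leukemia or active MDS before entry onto the protocol".
- **Follow-up clock.** Section 5.4: "Patients will be followed for relapse and death for three years from the first day of the first cycle of treatment".
- **Reference values.** Section 9.2 assumes historical two-year RFS of 40%, 34% and 20% in the myeloablative, non-myeloablative and consolidation arms. The corresponding rates are 0.46, 0.54 and 0.80 per person-year. It does not state the origin from which these were measured.

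**The concern.** A patient in CR2 has, by definition, already relapsed after CR1. If the origin is taken as the CR1 marrow, the first relapse after it precedes enrolment. The analyst must then choose between two readings that the plan does not address: score a relapse that happened before the trial, or ignore it and credit the patient with the whole of CR1 plus re-induction as relapse-free time. The first lowers the arm's RFS and the second raises it.

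Two-year RFS in each arm is the primary result. It is judged against a fixed historical value with no concurrent control, so an error in the clock goes straight into the conclusion. The futility looks in section 9.4 use one-year RFS. If the CR1 relapse is ignored, a patient whose current remission began more than a year after CR1 cannot fail at that landmark.

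The rest of the plan appears to count from about enrolment. Section 5.4 does so explicitly. Section 9.4 expects 20 patients by the time the first enrolled patient reaches two years, at 10 per arm per year. Since 20 / 10 = 2 years, that statement works only if the two years begin at about entry.

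**Working it through.** **1. The plan's own figures.** Under an exponential model, rate = -ln(S(2)) / 2.

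- Myeloablative: -ln(0.40) / 2 = 0.458 (stated 0.46)
- Non-myeloablative: -ln(0.34) / 2 = 0.539 (stated 0.54)
- Consolidation: -ln(0.20) / 2 = 0.805 (stated 0.80)

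The medians, ln 2 / rate, are 1.51 years, 1.28 years and 10.3 months, against 1.5 years, 1.3 years and 10.4 months in section 9.4. The stated figures reproduce.

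**2. Assumptions that the documents do not supply.** Let q be the CR2+ share of an arm (10, 20 or 30%). Let g be the time from the CR1 marrow to the current remission (1.5 years, range 1 to 2). RFS from the current remission is taken to follow the arm's null exponential for all patients, including CR2+.

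**3. CR1 relapse ignored, clock started at CR1.** A CR2+ patient passes the two-year mark by staying relapse-free for only 2 - g years of the current remission, with probability S(2)^((2 - g)/2). At g = 1.5 this is 0.40^0.25 = 0.795, 0.34^0.25 = 0.764 and 0.20^0.25 = 0.669. At g = 2 it is 1.

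Apparent arm RFS = (1 - q) × null + q × S(2)^((2 - g)/2). For the myeloablative arm at q = 20%: 0.8 × 0.40 + 0.2 × 0.795 = 0.479.

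| Arm (null) | q = 10% | q = 20% | q = 30% |
|---|---|---|---|
| Myeloablative (0.40) | 0.440 (0.423–0.460) | 0.479 (0.446–0.520) | 0.519 (0.470–0.580) |
| Non-myeloablative (0.34) | 0.382 (0.364–0.406) | 0.425 (0.389–0.472) | 0.467 (0.413–0.538) |
| Consolidation (0.20) | 0.247 (0.225–0.280) | 0.294 (0.249–0.360) | 0.341 (0.274–0.440) |

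The ranges are for g = 1 to 2 years.

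**4. Effect on a decision.** The plan states no final rejection threshold, so this is only an illustration. Take a rule of at least 14 of 25 patients relapse-free at two years in the myeloablative arm, with all 25 evaluable. Its false-positive rate is 0.078 at a true 0.40. At g = 1.5 it becomes 0.16 with q = 10% and 0.27 with q = 20%.

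**5. Effect on the interim landmark.** Null one-year RFS in the myeloablative arm is 0.40^0.5 = 0.632. With g of at least 1 year and q = 20%, it reads 0.8 × 0.632 + 0.2 × 1 = 0.706.

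**6. CR1 relapse counted as the event.** If every CR1 ended within two years, CR2+ patients contribute no two-year survivors. At q = 20% the arms read 0.8 × 0.40 = 0.32, 0.8 × 0.34 = 0.272 and 0.8 × 0.20 = 0.16.

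**7. Time between origin and entry, for any patient.** Even an origin at the end of definitive therapy leaves 60 to 185 days in which an enrolled patient cannot have failed. For the myeloablative arm, 60 days is 0.164 years and 185 days is 0.507 years. Then exp(-0.458 × (2 - 0.164)) = 0.431 and exp(-0.458 × (2 - 0.507)) = 0.504, against 0.40. Choosing the right remission is therefore not enough; the time at risk must also begin at enrolment.

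**The case against.** The best counter-argument is grammatical. In section 9.1.1 *first* qualifies *marrow*, and the text does not say CR1 or initial induction. Re-induction is also induction, so the origin could be the first marrow showing the remission that led to definitive therapy. The objective in 9.1.1, which speaks of patients in remission after definitive therapy, fits that reading, and on it no CR2+ patient is misdated. This stands as a possible reading, and it rules out the inference that every CR2+ patient has a wrong endpoint from enrolment. It does not settle the matter, because the rule is not written and the literal one points elsewhere.

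Three other stronger inferences are also unsupported.

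- The figures in step 6 should not be read as likely results. Patients must be free of leukaemia at entry and are followed from cycle 1, so an analyst is unlikely to score an earlier relapse. The figures also need every CR1 to have lasted under two years.
- A reader might infer that patients with detectable disease at transplant or consolidation have no remission marrow to date from. Criterion 4 of section 3.1 requires a clear marrow after therapy, so every eligible patient has one. What remains is that patients in one arm may be dated from different milestones.
- Delayed entry alone does not cure the literal reading. It would stop the credit for time before entry, but the clock would still belong to the wrong remission. A patient entering more than two years after CR1 would add nothing to the two-year estimate.

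The size is also open to challenge. The share and the gap are assumed, and CR2+ patients are given the arm-average hazard. If their hazard is higher, the inflation is smaller for gaps under two years.

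**Conclusion.** The primary endpoint is under-specified for an eligible subgroup, and the literal rule gives those patients wrong times. The more plausible error is upward. With the CR1 relapse ignored and a 1.5-year gap (range 1 to 2), an inactive drug shows about 44% at a 10% CR2+ share and 48% (45 to 52%) at 20% in the myeloablative arm, against 40%. At 20% the other arms show about 42% against 34% and 29% against 20%. These are illustrations; the documents give neither the share nor the gap, and the effect scales directly with the share. With no CR2+ patients enrolled, or with the current-remission reading applied throughout, this particular error disappears.

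The documents do not show that the sponsor intends the CR1 reading, and admitting CR2+ patients is not itself a fault. The wording should still be settled before analysis, because choosing the origin after outcomes are known would undermine an uncontrolled comparison.

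**What to change.** In section 9.1.1:

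1. Start RFS at the first marrow documenting the remission in which the patient is enrolled. Where there was no earlier remission in that course of treatment, use the marrow after definitive therapy.
2. Count patients as at risk only from enrolment (delayed-entry Kaplan-Meier).
3. State that relapses before that remission are not events.
4. Record remission number at entry.

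Before analysis, confirm that the historical 40%, 34% and 20% use the same origin, or restate them. If enrolment or first dose is preferred as the origin, the historical values must be re-based to match. That move is not free: it takes failures before entry off the trial's clock, and it would favour the drug in all patients if the references run from remission or transplant.

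The cost is a short amendment, one baseline field that eligibility review already needs, and a check of the historical sources. With 25 patients per arm, the early risk sets under delayed entry will be small, and the estimate is conditional on being relapse-free at the earliest entry time. The report should say so.
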